## 5 Sample Size

We expect the absolute difference in proportions of bacteriological confirmation between the two arms to be 7% (from 19% to 26% from the control to the intervention arm). Sample size was chosen to be sufficient to detect a 36.8% relative increase in the primary outcome in the intervention arm (as compared to the control arm).

Under this premise and the following assumptions:

- Alpha (two sided): 0.05
- Beta (power 80%): 0.2
- Estimated proportions of participants with microbiologically confirmed TB in the control arm 19% and in the intervention arm 26%
- Lost to follow up: 5% of recruited participants.

The study will recruit 586 PLHIV participants per trial arm, then we will include in the analysis 1172 participants in total. This number of participants will come from 4 sites (293 participants per arm at each site).

For this calculation we have used the following formulas based on Normal asymptotic approximation for proportions:

Sample Size formula

$$n_1 = \frac{\left( Z_{1-\alpha/2} \sqrt{(1 + \varphi) \bar{p}_1 (1 - \bar{p}_1)} + Z_{1-\beta} \sqrt{\varphi p_1 (1 - p_1) + p_1 (1 - p_1)} \right)^2}{\varphi |p_1 - \bar{p}_1|^2}$$

Power formula

$$\varphi = \frac{1 - w_1}{w_1}$$

$$\bar{p} = \frac{p_1 + \varphi p_2}{1 + \varphi}$$

$$1 - \beta = \Phi \left( \frac{|p_1 - \bar{p}| \sqrt{\varphi w_1} - Z_{1-\alpha/2} \sqrt{(1 + \varphi) \bar{p} (1 - \bar{p})}}{\sqrt{\varphi p_1 (1 - p_1) + p_2 (1 - p_2)}} \right)$$

## 6 General Considerations

### 6.1 Timing of Analyses

The analysis will be done after database lock and the data cleaning process is finalized.

We will analyse the data using primarily an intention to treat (ITT) analysis approach. This dataset will be composed for all randomized participants by their assigned intervention independent of participation time of this participants in the study. Also, we will analyse the results using the Per Protocol Population approach.

#### 6.1.1 Per Protocol Population

For the primary and some secondary endpoints, we will be using the set of data defined as “per-protocol” (PP). This dataset we will only include participants with all required samples collected and results available within 72 hours from enrolment.

This can shed light on a potential effect of poor adherence to study protocol procedures on the primary and secondary endpoints.

### 6.2 Missing Data

Given the characteristics and design of the trial (including data monitoring activities) we expect a low proportion of missing variables.

We will analyse the mechanisms that cause missing data. We plan to identify the three typical patterns for missing data: missing completely at random (MCAR); missing at random (MAR); and missing not at random (MNAR).

To assess the potential influence of missing values in intervention related variables or visit related variables (due to withdraws or death), we will compare the results of the ITT and per protocol analyses. To assess the potential influence of missing values in endpoint related

---

variables, we will perform a complete case analysis when the proportion of missing data is below, approximately, 5% and it is implausible that certain patient groups specifically are lost to follow-up in one of the compared arms. In this case we will analyse previously if the missing data are random or follow some pattern.

For missing data over 5%, we will do a worst/best scenario sensitivity analysis for the main endpoint related variables (related TB treatment initiation, time from enrolment and microbiological results). This consists of assigning the best plausible outcome to the above endpoint-related missing values in both arms (i.e TB treatment started, TB treatment started before 72 hours from enrolment, or TB microbiological confirmation) and the other assigning the worst possible outcome to all missing values in both groups (TB treatment not initiated, TB treatment started after 72 hours from enrolment, non-TB microbiological confirmation).

We will also compare the results of one assigning the best possible outcome to missing values in the intervention arm and the worst possible to those of the intervention arm, and vice-versa.

If this sensitivity analyses raise inconsistent results on the intervention effect, their repercussions will be discussed between the statisticians involved in trial analysis.

### 6.3 Multiple Testing

We consider unnecessary to apply a general adjustment of significance level by multiple comparisons test. We will use the all the statistical power for inference only in the primary study objective. To evaluate the other study endpoints, we use the p-value threshold at 0.05 to find the differences in our study without the objective to extrapolate the results to the global community. However, we will establish a p-value of 0.01 as a threshold for statistical significance in the comparisons related to a) selected secondary efficacy analyses (section 8.2, analyses 8.2.5, 8.2.6, 8.2.7) and subgroup analysis (see section 9.0)

We will adjust the results by site, demographic variables, and other baseline variables if we will detect differences or if these variables have a confounder characteristics profile. To decide this, we will do a preliminary analysis of these variables between sites.

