The primary efficacy endpoint has a composite numerator 'microbiologically confirmed TB and therapy initiated within 72 hours from admission' (success), 'non lab-confirmed TB or therapy

This project is part of the EDCTP2 programme supported by the European Union

not initiated within 72 hours' (failure).

Microbiological confirmation may arrive later than 72 hours after enrolment (to account for scenarios in which culture is requested or there is any delay on sample processing).

The primary efficacy analysis will be compared between the proportion of microbiologically confirmed TB and therapy initiated within 72 hours of enrolment in each study arm.

Adjustment for other variables (country, hospital, seasonality or other possible confounders) may be considered and will be described in detail in the analysis plan.

Missing values will be examined in detail. We may consider a multiple imputation procedure if necessary (variables with more than 10% of missing values).

We will accept as significant difference the p-values less than 0.05.

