## 9. Subgroup analysis

The analysis of all endpoints will be done for all patients of both countries as sample size did not take into consideration country-specific analyses of the specified primary endpoint. Thus, we will merge the data from the four sites we will analyse the resulting database as unique source of data.

However, a subgroup analysis of the primary endpoint and main secondary endpoint (mortality at month 2) will be done by study site (Mozambique and Tanzania, CD4 counts and viral load).

A separate analysis of the primary and secondary endpoints will also be performed by sex of participants, in order to assess if differences arise in any of the outcomes.

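### The SAP makes covariate adjustment depend on a preliminary look at the data and does not say whether the unadjusted or an adjusted result is primary; one fixed model should be named.

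*SAP*

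**What the plan says.** SAP 8.1 defines the primary analysis as the difference between arms in the proportion with confirmed TB who started treatment within 72 hours, tested with a z-statistic. No covariates enter that test. It adds that the comparison will be stratified by country and baseline CD4, without saying whether this means subgroup results or one pooled stratified estimate.

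SAP 6.3, under multiple testing, then says "We will adjust the results by site, demographic variables, and other baseline variables if we will detect differences", or if a variable has the profile of a confounder. The method of choice follows: "To decide this, we will do a preliminary analysis of these variables between sites". The rule covers the results in general. It gives no closed list of variables, threshold, model or effect measure.

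SAP 9 says "we will merge the data from the four sites we will analyse the resulting database as unique source of data".

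Protocol 13.2.2, on the primary efficacy analysis, says "Adjustment for other variables (country, hospital, seasonality or other possible confounders) may be considered and will be described in detail in the analysis plan". The same section has a second trigger: if any baseline attribute is significantly related to loss to follow-up, the analysis is adjusted for it.

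SAP 8.2.7 is the only analysis with a fixed covariate set (site, sex, CD4). It is a secondary time-to-event model.

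**The concern.** The criterion does not fit the purpose. Participants are randomised individually. That patients at one site are older or more immunosuppressed than at another says nothing about whether the arms differ within sites, so it cannot identify confounding of the arm comparison.

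The rule is also not mechanical. No significance threshold is given, and judging whether a variable resembles a confounder is open to opinion. The inputs are loose as well:

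- **Site.** This means two countries in SAP 9 and four sites in SAP 5. Protocol 9.1.1 and 9.1.2 name at least seven hospitals, plus three optional health centres.
- **CD4.** It is cut at 100 in SAP 7.2, at 200 in SAP Table 1, and into three groups in SAP 11 that may be refined on the observed frequencies.
- **Symptoms in hospital.** SAP 4.4 assigns cough, fever, night sweats and weight loss during hospitalisation, all recorded after randomisation, to modelling without naming a model.

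The trial is unblinded (SAP 4.3) and was planned at 80% power. If the result is borderline, the primary conclusion could turn on a model chosen after the data were seen. The same wording covers 8-week mortality.

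**Working it through.** **1. The plan's sample size.** Inputs from SAP 5: "Alpha (two sided): 0.05"; "Beta (power 80%): 0.2"; 19% against 26%; 5% loss. With pooled proportion 0.225:

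n = [1.960·√(2·0.225·0.775) + 0.8416·√(0.19·0.81 + 0.26·0.74)]² / 0.07² = 557.5, so 558 per arm.

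558 × 1.05 = 585.9, so 586. (Dividing by 0.95 gives 588.) The stated 586 reproduces.

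**2. Precision from a fixed adjusted analysis.** The intention-to-treat set is all randomised, so 586 per arm is used.

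- Unadjusted SE = √[(0.1539 + 0.1924)/586] = 2.43 points; 95% half-width 4.76 points.
- Power = Φ[(0.07·√586 − 1.1575)/0.5885] = Φ(0.913) = 81.9%.

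If covariates explain a share R² of outcome variance, the variance falls by the factor 1 − R², so n becomes 586/(1 − R²). The documents give no R², so a range is assumed:

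| Assumed R² | Half-width (points) | Power |
|---|---|---|
| 0 | 4.76 | 81.9% |
| 2% | 4.72 | 82.7% |
| 5% | 4.64 | 83.8% |
| 10% | 4.52 | 85.7% |

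**3. Type I error.** Simulation with 1172 participants, 1:1 allocation, true rate 19% in both arms, and site plus six baseline covariates of assumed weak, moderate or strong effect. Each scenario had 1500 trials, so the Monte Carlo error is about 0.6 points near 5%. Two-sided rejection rates:

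| Analysis | Weak | Moderate | Strong |
|---|---|---|---|
| Unadjusted | 4.6% | 6.1% | 5.1% |
| Pre-specified site + CD4 | 4.3% | 6.9% | 5.0% |
| Site plus whatever differs between sites at p < 0.05 | 4.4% | 6.7% | 5.1% |
| Any of 2⁷ = 128 covariate sets | 5.9% | 11.0% | 12.0% |

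The moderate runs were high for every method, the unadjusted test included, so compare within columns. The third row is the between-site rule applied mechanically, with a threshold the SAP does not state. The last row is the ceiling if the most favourable p-value were always reported. With a true 7-point difference, the pre-specified model averaged about 7.0 points, so it was unbiased.

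The scope for choice is large. SAP 10 lists 14 baseline variables. Dropping TB treatment start and adding CD4 leaves 14, hence 2¹⁴ = 16,384 main-effect covariate sets.

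**4. Whether CD4 can be used.** The footnote to the protocol's schedule of visits has CD4 tested in everyone without a count in the last 3 months. Protocol 12.4 has counts obtained from TB cases without a recent count and from newly identified HIV-positive cases. Under the second statement, having a count depends on the outcome.

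To see the effect, suppose every TB case has a CD4 count and a share s of the others do. The missing-CD4 group then has no events. A logistic model with arm and a missing-CD4 category returns the difference among those with a count, multiplied by the overall fraction with a count. For s = 0.3:

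- control: 0.19/(0.19 + 0.81·0.3) = 0.439
- intervention: 0.26/(0.26 + 0.74·0.3) = 0.539
- fraction with a count: (0.433 + 0.482)/2 = 0.4575
- estimate: 0.1006 × 0.4575 = 4.6 points, against a true 7.0

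The same steps give 5.7 points for s = 0.5 and 6.4 for s = 0.7. Simulation that also included assumed CD4 strata gave about 4.4, 5.4 and 6.3. The values of s are assumptions.

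**The case against.** The strongest reply is that the primary analysis is already defined. SAP 8.1 gives an unadjusted difference, a z-test and the p-value formula, and SAP Table 4 has one risk difference and one p-value with no adjusted column. An unadjusted test is valid in a randomised trial, and the sample size was built for it. The protocol says only that adjustment may be considered. On this view one line calling adjusted results secondary is enough.

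Much of this stands. The unadjusted test is valid, and naming it as the sole primary result would also remove the ambiguity, at the price of the precision in step 2. What does not stand is that the documents already do so. SAP 6.3 refers to the results without exception, SAP 8.1 does not claim precedence, and the protocol places possible adjustment inside the primary efficacy analysis and leaves the detail to a SAP that does not give it.

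A reader might infer that the SAP permits picking the smallest p-value, or that the between-site rule itself inflates type I error. Neither is supported. No text allows selection by p-value, and the mechanical rule tracked the unadjusted test. A reader might also infer that site and CD4 are ignored. SAP 8.1 does mention stratifying by country and CD4; its meaning is unclear, but it is not absent.

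**Conclusion.** The point holds as a defect of specification. The primary result is not uniquely defined, because a data-dependent adjustment rule stands beside an unadjusted test with no order between them, and the criterion for adjusting is irrelevant to confounding in this design.

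The risk comes from discretion, not from the between-site comparison as such. Rejection rates of about 6% to 12% bound the harm under free choice and assumed covariate strengths; the actual rate cannot be known from the documents. The precision argument is secondary: at 586 per arm, 0.8 to 3.8 points of power for an assumed R² of 2% to 10%. It would be too strong to say that the trial is underpowered without adjustment, since unadjusted power at the planned rates is 81.9%. It would also be too strong to say that adjusting for CD4 is safe as the protocol stands, because step 4 shows a possible bias towards no difference.

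**What to change.** 1. Delete the two adjustment sentences in SAP 6.3. Remove the loss-to-follow-up trigger in Protocol 13.2.2 as it applies to the primary analysis.
2. In SAP 8.1 name one primary estimate: the arm-standardised risk difference from a logistic model with arm and the four recruiting sites as fixed terms, with a robust or unconditional standard error. In Stata this is a logit fit followed by margins with unconditional variance. Define site as the four sites; individual hospitals could give sparse cells.
3. Reconcile the schedule-of-visits footnote with Protocol 12.4 on who has a CD4 count. If CD4 is then a pre-randomisation value whose availability does not depend on TB diagnosis, add it to the model in one stated categorisation, with its missing-value handling stated. If not, adjust for site only.
4. Name the unadjusted z-test as the supportive analysis. State that no baseline, between-site or loss-to-follow-up testing selects covariates for the primary analysis.
5. Say whether the stratification in SAP 8.1 means subgroup results.

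The cost is SAP wording, a matching protocol clarification and a few lines of Stata. No new data are needed for the site-only model. The changes should be dated before anyone sees outcome data by arm.

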## 7 Summary of Study Data

### 7.1 Subject Disposition

We will use the **Study Completion, Withdrawal and Drop-out Form (TB-CAPT-HIV EXULTANT-StudyCompletion-v3.1)** to show how many participants reached the study stages. Data from this form, **from question 1 to 4**, will allow us to know the number of dropouts and their reasons and how many participants will arrive to week 8 or not.

## 7.2 Derived variables

We will create some derived variables according to solve the study hypothesis, some of them we will describe in the following SAP versions.

The variables that we will create are:

New Variable	Type	Values
Type of Employment	Categorical	0: Unemployed for any reason 1: Health care worker 2: Prison warder or work at a correctional facility 3: Miner
Time from last HIV+ result	Continuous	0 to randomization date
Time of follow-up	Continuous	From randomization date to end study completion date
Time to TB treatment initiation (in hours)	Continuous	From randomization date to start TB treatment date
ITT cohort	Categorical	0: Not included in ITT 1: Included in ITT
ATP cohort	Categorical	0: Not included in ATP 1: Included in ATP
Participants diagnosed with microbiologically confirmed TB	Categorical	0: No 1: Yes
Participants diagnosed with microbiologically confirmed TB and started on TB treatment within 72 hours of enrolment	Categorical	0: No 1: Yes
CD4 (binary)	Categorical	0: CD4 count <100

	1: CD4 count >=100
--	--------------------

## 8 Efficacy Analyses

### 8.1 Primary Efficacy Analysis

The primary efficacy is defined as the difference in the proportion of microbiologically confirmed TB and therapy initiated within 72 hours from enrolment in the intervention and control arm. (the comparison by estimating the difference of proportions and see whether is significantly differs from zero)

We will compare the difference of proportions, defined above, between both study arms and see if the results are significantly different from zero. We will test this differences using the test statistics  $z$  has an asymptotic standard normal distribution, and the p-value will be computed as:

$p = 2 \{1 - \Phi(|z|)\}$  where  $\Phi(\cdot)$  is the cdf of a standard normal distribution and  $|z|$  is an absolute value of  $z$ . We will calculate logit-transformed 95% confidence intervals

We will compare this proportion as a risk difference and we will stratify by study countries, baseline CD4 counts (under the hypothesis the highest difference in % of bac confirmed participants between control and intervention arm will occur in those immunosuppressed ones, or in countries with highest % of immunosuppressed admitted participants).

We will evaluate the primary efficacy analysis by ITT and Per protocol populations. We will show the both results in the final analysis document with the correspondent tables and graphs.

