The limitations of existing sputum-based tests for *M. tuberculosis* (Mtb) diagnosis among (PLHIV) admitted to hospital create imperatives to explore the usefulness of easy to collect, non-respiratory specimens which could improve TB diagnosis, while supporting and accelerating treatment guidance. Previous studies have shown that Xpert testing of urine and stool can confirm Mtb in participants who would otherwise test negative with traditional sputum-based methods. Evidence shows that these diagnostics may detect additional cases that are not detected by AlereLAM. Thus, an algorithm using the different tests (sputum Ultra, urine Ultra and stool Ultra) offered as a screening intervention to admitted HIV positive participants should increase the Mtb bacteriological yield (compared to current WHO recommended screening and testing strategies\*\*) and contribute to earlier initiation of TB treatment. Given that some detected cases may not present with classical TB symptoms at the time of hospitalization, we believe that this strategy will increase the overall number of participants with diagnosed TB and started on treatment and ultimately reducing mortality.

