## 11 Reporting Conventions

We will use two decimals in numeric results. We will round to up the value of second decimal when the third decimal value will be equal or higher than 5, in other cases we will do nothing.

All confidence intervals (CI) will be calculated at 95% of confidence. These will be calculated using the logit-transformed confidence interval method. We will use the Haybittle-Peto approach for the evaluation of the p-value, under this approach we will consider statistically significant when the p-value's test is lower than 0.05 in the final analysis

Where necessary, variables will be categorized using the cut-off described in previous works and research publish documents. For example, CD4 counts will be categorized in 3: less than 100 CD4 counts per ml (as in STAMP trial), 100-200 CD4 counts per ml, and above 200.

However, depending on the frequencies observed, these categories could be refined. When we don't have a reference cut-off value for a continuous variable, we will calculate these values using the terciles, quartiles or quintiles of the variable and cut it using this calculated cut-off values. (For example, if we want to divide the participants age in three categories, we will calculate the terciles values and later we calculate a new categorical variable using these points. Then we will have a new age group with three categories: from minimum value to first tercile, from first to second tercile and finally from second tercile to maximum value).

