	ITT Analysis			Per Protocol Analysis		
	Standard-of-care group (n=XXXX)	Intervention group (n=XXXX)	p-value	Standard-of-care group (n=XXXX)	Intervention group (n=XXXX)	p-value
Samples available	XXX (XX.X)	XX.X (XX.X)	X.XXX	XX.X (XX.X)	XX.X (XX.X)	X.XXX
Sputum Ultra available	XXX (XX%)	XXX (XX%)	X.XXX	XXX (XX%)	XXX (XX%)	X.XXX
Sputum Ultra results						
Negative	XXX (XX%)	XXX (XX%)	X.XXX	XXX (XX%)	XXX (XX%)	X.XXX
Indeterminate	XXX (XX%)	XXX (XX%)		XXX (XX%)	XXX (XX%)	
Positive	XXX (XX%)	XXX (XX%)		XXX (XX%)	XXX (XX%)	
Urine Ultra available		XXX (XX%)			XXX (XX%)	
Urine Ultra results						
Negative		XXX (XX%)			XXX (XX%)	
Indeterminate		XXX (XX%)			XXX (XX%)	

Positive		XXX (XX%)			XXX (XX%)	
Stool Ultra available		XXX (XX%)			XXX (XX%)	
Stool Ultra results						
Negative		XXX (XX%)			XXX (XX%)	
Indeterminate		XXX (XX%)			XXX (XX%)	
Positive		XXX (XX%)			XXX (XX%)	
AlereLAM available	XXX (XX%)			XXX (XX%)		
AlereLAM results						
Negative	XXX (XX%)			XXX (XX%)	XXX (XX%)	
Indeterminate	XXX (XX%)			XXX (XX%)	XXX (XX%)	
Positive	XXX (XX%)			XXX (XX%)	XXX (XX%)	
Microbiologically confirmed	XXX (XX.X)	XX.X (XX.X)	X.XXX	XX.X (XX.X)	XX.X (XX.X)	X.XXX

Table 3. TB treatment initiation within 72 hours

	ITT Analysis			Per Protocol Analysis		
	Standard-of-care group (n=XXXX)	Intervention group (n=XXXX)	p-value	Standard-of-care group (n=XXXX)	Intervention group (n=XXXX)	p-value
Start treatment within 72 hours	XXX (XX.X%)	XXX (XX.X%)	X.XXX	XXX (XX.X%)	XXX (XX.X%)	X.XXX
Hours to start treatment (treatments <= 72h)	XXX (XX%)	XXX (XX%)	X.XXX	XXX (XX%)	XXX (XX%)	X.XXX

Days to start treatment (treatments > 72h)	XXX (XX%)	XXX (XX%)	X.XXX	XXX (XX%)	XXX (XX%)	X.XXX
Start treatment within 72 hours						
Confirmed TB	XXX (XX%)	XXX (XX%)	X.XXX	XXX (XX%)	XXX (XX%)	X.XXX
Unconfirmed TB	XXX (XX%)	XXX (XX%)	X.XXX	XXX (XX%)	XXX (XX%)	X.XXX

Table 4 TB outcomes at 8 weeks by arm (ITT analysis)

	Standard-of-care group (n=XXXX, %)	Intervention group (n=XXXX, %)	Risk Difference % (95% CI)	p-value
Start treatment within 72 hours	XXX (XX.X)	XX.X (XX.X)	X.X (X.X, X.X)	X.XXX
Microbiologically confirmed TB	XXX (XX%)	XXX (XX%)	X.X (X.X, X.X)	X.XXX
Clinically diagnosed TB	XXX (XX%)	XXX (XX%)	X.X (X.X, X.X)	X.XXX
Deaths at week 8	XXX (XX%)	XXX (XX%)	X.X (X.X, X.X)	X.XXX

Figure 1. Trial flowchart

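### SAP 8.1 and section 11 prescribe logit-transformed 95% confidence intervals for everything, but the primary effect and Table 4 are risk differences, for which no suitable interval method is stated

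*SAP*

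**What the plan says.** - **SAP 8.1** defines primary efficacy as the between-arm difference in the proportion with confirmed TB who start treatment within 72 hours, and tests it against zero with a two-sided z-test. The paragraph that describes the test ends: "We will calculate logit-transformed 95% confidence intervals". The next paragraph begins: "We will compare this proportion as a risk difference".
- **SAP section 11** sets the rule for the whole analysis: "All confidence intervals (CI) will be calculated at 95% of confidence", followed by "These will be calculated using the logit-transformed confidence interval method".
- **SAP section 13, Table 4** has a column headed "Risk Difference % (95% CI" for four rows: treatment start within 72 hours, microbiologically confirmed TB, clinically diagnosed TB, and "Deaths at week 8".
- **SAP 8.2.7** calls for hazard ratios, whose intervals also fall under the section 11 rule.
- **Protocol 13.2.2** names tests but no interval method. No section of either document gives a method for the interval of a difference between proportions.

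**The concern.** The logit, log(p/(1-p)), exists only for values strictly between 0 and 1. It suits a single proportion. A risk difference can lie anywhere from -1 to 1, so a logit interval applied to it fails in two ways:

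- At zero or below, the logit does not exist and there is no interval.
- Above zero, both back-transformed limits are positive. The interval excludes zero however weak the evidence, and so conflicts with a non-significant z-test.

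The deaths row is the clearest case. The SAP preface hopes for more participants "started on treatment and ultimately reducing mortality", and SAP section 5 describes the expected effect as "from 19% to 26% from the control to the intervention arm". If Table 4 also takes intervention minus control, the hoped-for mortality difference is negative and the rule yields nothing. The SAP does not state that order. Under the opposite order the same difficulty would move to the primary endpoint, where the hoped-for difference would be negative.

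At stake is the stated precision of the primary effect and of the mortality difference, and whether the rule for it is fixed before the data are seen. The trial is unblinded (SAP 4.3), which is a further reason to settle the method in advance.

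**Working it through.** **Inputs.** 586 per arm, 19% control and 26% intervention, two-sided alpha 0.05 and 80% power are from SAP section 5. The +3-point case, the stratum sizes and the death rates are assumptions, chosen for illustration.

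**Step 1: reproduce the plan's figure.** The pooled-variance formula for 19% v 26% gives 557.5, so 558 per arm. Multiplying by 1.05 gives 558 x 1.05 = 585.9, or 586, the SAP figure. Dividing by 0.95 gives 588. The interval question does not touch this calculation.

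**Step 2: standard intervals for the difference.** With p1 = 0.19, p2 = p1 + d and n = 586:

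- Wald: d +/- 1.96 x SE, where SE = sqrt(p1(1-p1)/n + p2(1-p2)/n). SE is 0.0243 at d = 0.07 and 0.0236 at d = 0.03.
- Newcombe: combines the two arms' Wilson limits.
- Miettinen-Nurminen: score limits with constrained maximum-likelihood estimates and variance factor N/(N-1).

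| Difference (points) | Wald | Newcombe | Miettinen-Nurminen |
|---|---|---|---|
| +7 | 2.24 to 11.76 | 2.22 to 11.74 | 2.22 to 11.77 |
| +3 | -1.62 to 7.62 | -1.63 to 7.61 | -1.63 to 7.63 |

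The methods agree to within 0.03 points.

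**Step 3: the same methods in smaller strata.** SAP 8.1 stratifies by country and CD4 count. At 19% v 26% the largest spread between the three methods is 0.05 points with 293 per arm, 0.20 with 100 and 0.48 with 50.

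**Step 4: the rule applied literally to the difference.** The SAP gives no formula. One delta-method form is logit(d) +/- 1.96 x SE/(d(1-d)), back-transformed. The z-test below uses the pooled variance; SAP 8.1 does not say pooled or unpooled.

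- d = 0.03: logit = -3.476; SE/(d(1-d)) = 0.02357/0.0291 = 0.810; limits 0.63 to 13.14 points. z = 1.27, p = 0.203. The interval excludes zero and the test does not reject.
- d = 0.07: logit = -2.587; SE/(d(1-d)) = 0.02431/0.0651 = 0.373; limits 3.5 to 13.5 points. z = 2.87, p = 0.004. Both exclude zero, but the interval still differs from the 2.2 to 11.8 of the standard methods.
- d = 0 or below: no interval.

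**Step 5: how often the deaths row would have no interval, read literally.** The documents give no expected death rate. For two independent binomials with 586 per arm and intervention minus control, the chance that the observed difference is zero or negative is:

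| Assumed deaths, control v intervention | Chance of no logit interval |
|---|---|
| 10% v 8% | 89% |
| 15% v 12% | 94% |
| 20% v 17% | 91% |
| 20% v 15% | 99% |

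**Step 6: the per-arm reading.** Logit intervals for each arm at 19% and 26% are 16.0 to 22.4% and 22.6 to 29.7%. They are well defined, but they are intervals for two proportions and not for their difference.

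**The case against.** The strongest reply is that the logit intervals were meant for each arm's own proportion. SAP 8.1 is open to that reading, since the risk difference is introduced only in the next paragraph. Nothing is then undefined, and the figures in steps 4 and 5 do not apply. Per-arm logit limits can also be combined into an interval for the difference by the MOVER method, with no difficulty over negative values: 2.21 to 11.75 at +7 points and -1.63 to 7.62 at +3 points, close to the standard methods. This stands as far as it goes. A reader might infer that the SAP is impossible to follow, or that the analyst is bound to breach it; that is too strong. But the SAP states neither the per-arm restriction nor the combining step, and section 11 says all intervals. On this reading the difference simply has no specified method.

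A reader might also infer that a logit interval can never agree with the z-test. It can: at +7 points both exclude zero. The conflict arises when the observed difference is positive and the test is non-significant.

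Finally, the primary decision in SAP 8.1 is the z-test p-value, no interim decision depends on an interval (protocol 13.2.4 plans no formal interim analysis), and the choice among sound methods hardly moves the limits. All of that is right, and it limits the weight of the point.

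**Conclusion.** The point holds as a low-impact correction to a stated rule. Read literally, the rule gives wrong limits for a positive risk difference and none for a zero or negative one. Read charitably, it leaves the primary effect and all four rows of Table 4 without a named interval method.

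The documents do not support a stronger conclusion. The z-test, the sample size and the primary conclusion are unaffected. Choosing among standard methods changes the limits by about 0.03 points at 586 per arm, and by up to 0.48 points in an assumed stratum of 50 per arm. The statement about mortality depends on taking intervention minus control, which is inferred, and the percentages in step 5 rest on assumed death rates. The interval of 0.6 to 13.1 is a hypothetical illustration in a form that the SAP does not give.

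**What to change.** In SAP 8.1 and section 11:

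1. State that risk differences are intervention minus control, with one named 95% interval method (for example Newcombe, Miettinen-Nurminen or Wald).
2. Limit logit-transformed intervals to single-arm proportions.
3. Exempt hazard ratios, and use the usual log-scale interval from the Cox model for them. Without this, SAP 8.2.7 would either stay under a rule that does not suit it or have no stated method.

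Table 4 needs no change. The cost is a few sentences in two sections of the SAP, with no effect on data collection, sample size or the primary test.
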